7. STUDY DESIGN

This study is a mixed methods design. The quantitative study will be a randomised single blinded design. Up to 40 participants will be recruited from a single site at the Nuffield Orthopaedic Centre in Oxford. After recruitment baseline outcome measures will be taken. Block randomisation will then be used to balance stratification factors (hip or knee arthroplasty) into either the intervention or control group. The participant will receive their physiotherapy intervention or control at the Nuffield Orthopaedic Centre which will last up to 12 weeks. Once the first 5 participants randomised into the intervention arm have been recruited the study will be halted whilst all adverse event data is collected to ensure participants have not fallen when completing the intervention. If the study team is happy the intervention is not causing any adverse events, then the next five participants will be recruited and again the study will halt whilst their adverse event data is collected. This will continue until all 20 participants for the intervention group are recruited. Outcome measures will be repeated at 12 weeks once the treatment has ceased. This will be the final data collection point for the study.

The qualitative element of the study will involve semi structured interviews. This will take place after the participants have completed their 12 week follow up and physiotherapists have completed the intervention delivery. We will interview to a point of theoretical saturation¹⁶, and anticipate that up to 10 participants and 5 physiotherapists will allow us to develop useful themes.

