9. PROTOCOL PROCEDURES

9.1. Recruitment

Patients who have had a hip or knee replacement at the Nuffield Orthopaedic Centre in Oxford attend a 6 week post discharge clinic appointment. These patients will be screened for eligibility by their direct care team (Nuffield Orthopaedic Centre Physiotherapists). They will be introduced to the study by either a letter in the post from their direct care team (which will be sent alongside their clinic appointment letter) with information about the study and invitation letter and reply slip, or they will be introduced to the study and given the study information by their direct care team during their routine clinical appointment. Patients will be given ample time to consider taking part in the study. If they express an interest in the study the investigator will review the study details and answer any questions they may have. They will then be screened for eligibility and those who meet the criteria will take part in the study. If they agree to take part an appointment will be made to obtain consent and record baseline data and outcome measures with a trial research clinician at the Nuffield Orthopaedic Centre. Once patients have completed their baseline assessment they will be randomised according to the procedure set out below. Those who do not wish to take part will be asked if they can provide a reason for declining so that recruitment onto the trial can be analysed. The trial research clinician will also record the number of responders to the study information. As detailed in the study design section after the first 5 participants have been recruited to the intervention arm the study will stop whilst adverse event data is collected to ensure participants are not falling during the intervention. Providing this is not the case the study will resume and continue to stop and evaluate adverse event data for every 5 participants in the intervention arm.

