9.6. Description of study intervention(s), comparators and study procedures (clinical)

9.6.1. Description of study intervention(s)

This group will undertake a routine course of one to one out-patient physiotherapy which will include a BW programme. The BW programme will be prescribed by a physiotherapist and the participant will carry it out, along with other prescribed exercises, in their own home. Aside from the BW programme the physiotherapy treatments offered in the initial and review sessions will not be restricted but will be recorded in treatment logs. Each participant will initially be prescribed a 5 minute BW programme to be completed once a day. Participants will score the intensity of their backwards walking based on the BORG rating of perceived exertion scale. The aim will be for participants to be working at the light to somewhat hard level on the scale (11-14) (see appendix 1). The length of the BW programme and intensity will be progressed or regressed as deemed appropriate by the treating clinician with the aim for patients to achieve at least 10 minutes of BW every day of the week by the end of the programme. The

programme will be issued for completion over the course of 12 weeks and up to four review appointments will be made with the participant to monitor the BW programme and other prescribed exercises. To promote adherence a BW programme diary will be issued to participants to complete each time they carry out the programme in their own homes.

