The intervention was developed in line with the MRC developing complex intervention guidelines¹⁸. The guidelines state a three stage process should be used to develop interventions including identifying existing evidence, identifying and developing theory and modelling process and outcomes. The initial stage of identifying evidence was conducted by reviewing a recent literature review which appraised 11 studies with a backwards walking programme for musculoskeletal conditions¹³. The studies ran over no more than 4 weeks and each session lasted between 5 to 10 minutes. From this we surmised that as these patients would have recently had joint replacement surgery they may struggle with the intensity of a 10 minute programme used in other musculoskeletal conditions. It was determined therefore that initially the sessions should start at 5 minutes and that the treating therapists should clinically reason when to progress each participant up to the maximum 10 minute BW programme. All the studies were conducted in a supervised environment with some participants returning daily to complete the BW programme under supervision. This was not deemed feasible in an NHS setting where clinical resources are limited and so along with consultation from clinical specialists it was determined that the programme should initially be prescribed by a physiotherapist and once the patient could complete this safely this should be issued for completion at home over 12 weeks. This formed the identifying and developing theory process. The final stage is modelling and outcomes which will be tested in this feasibility pilot study.

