9.10. Early Discontinuation/Withdrawal of Participants

Each participant has the right to withdraw from the study at any time. In addition, the Chief Investigator (CI) may discontinue a participant from the study interventions at any time if the investigator considers it necessary for any reason including:

- Ineligibility (either arising during the study or retrospectively having been overlooked at screening)
- A significant protocol deviation
- A significant non-compliance with treatment regimen or study requirements
- An adverse event which requires discontinuation of the study intervention or results in inability to continue to comply with trial procedures

It will be the sole responsibility of the CI to determine whether investigator-led discontinuation occurs or not.

The treating clinician may withdraw a participant from the study if they feel it would not be clinically appropriate for them to continue.

If the participant has withdrawn from study treatment then they will be encouraged to continue with the follow-up.

Participants who wish to withdraw consent for the study or whose participation from the trial is discontinued will have de-identifiable data collected up to the point of that withdrawal of consent, included in the analyses, unless the participant specifically asks for all data collected to be destroyed. The participant will not contribute further data to the trial and the withdrawal CRF will be completed which documents the level of withdrawal. The reason for withdrawal will also be recorded. Participants who withdraw once they have been randomised will not be replaced.

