10.2. Reporting Procedures for Serious Adverse Events

A serious adverse event (SAE) occurring to a participant should be reported to the REC that gave a favourable opinion of the study where in the opinion of the Chief Investigator the event was 'related' (resulted from administration of any of the research procedures) and 'unexpected' in relation to those procedures. Reports of related and unexpected SAEs should be submitted within 15 working days of the Chief Investigator becoming aware of the event, using the HRA report of serious adverse event form (see HRA website).

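### The only required study-level safety halt follows a recruitment count of five, so a known injurious backwards-walking fall or possibly related SAE between counts does not itself prompt a review

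*Combined protocol and SAP*

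**What the plan says.** Section 7 (Study Design) halts the study once five people have been recruited to the intervention arm. The stated purpose is "to ensure participants have not fallen when completing the intervention". If the study team is satisfied, "then the next five participants will be recruited and again the study will halt whilst their adverse event data is collected", and so on until all 20 are in. Section 9.1 (Recruitment) restates this: the study will "continue to stop and evaluate adverse event data for every 5 participants in the intervention arm". Neither section gives a halt length or adds a trigger based on an event.

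The other safety provisions are narrower:

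- Section 9.6.1: "up to four review appointments will be made with the participant to monitor the BW programme and other prescribed exercises".
- Section 9.10: the Chief Investigator may discontinue an individual, one ground being "An adverse event which requires discontinuation of the study intervention or results in inability to continue to comply with trial procedures". The treating clinician may also withdraw a participant.
- Section 10: related SAEs are followed until they resolve or stabilise.
- Section 10.2: "Reports of related and unexpected SAEs should be submitted within 15 working days of the Chief Investigator becoming aware of the event".
- Sections 13 to 13.3: monitoring or audit is possible but not required, there is no formal risk assessment plan, study monitoring is marked not applicable, and there is no oversight committee.

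On the evidence behind the programme, section 9.6.1 says of the reviewed trials: "The studies ran over no more than 4 weeks and each session lasted between 5 to 10 minutes". It adds: "All the studies were conducted in a supervised environment with some participants returning daily to complete the BW programme under supervision".

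**The concern.** The halts exist to find out whether people fall while walking backwards, yet such a fall does not itself start a review. If the second of five recruits has an injurious fall at home, the rule as written lets allocation continue until the fifth is in.

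The wording leaves a second gap. The first halt collects all adverse event data. Later halts are worded to collect the data of the five just recruited. A late fall by someone from a previous batch, still within the 12 weeks, may then belong to no scheduled review.

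This matters more than it would for a well-tested programme. The reviewed studies were supervised and short, whereas this trial asks people aged 65 or over to practise daily at home for 12 weeks soon after joint replacement. An injurious fall therefore tells the team something about the programme as well as about the person who fell. With no committee and no required monitoring, the count-based halt is the only mandated study-level check.

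**Working it through.** **Does any other provision fill the gap?** Each was read for a required study-level pause or review after an event.

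- Review appointments (9.6.1), discontinuation and withdrawal (9.10) and SAE follow-up (10) concern one participant.
- REC reporting (10.2) applies only to an SAE judged both related and unexpected, and leads to a report rather than a pause. An injurious fall that is not serious under 10.1 is outside it.
- Fidelity checks (9.8) look at adherence to the protocol.
- Serious-breach reporting (15) does not cover a fall as such.

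None requires a study-level review.

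**Inputs**

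- Intervention arm of 20, halt every 5 (sections 7 and 9.1): 20/5 = 4 batches. The arm size agrees with section 11.3: 2 × 20 = 40.
- Programme length: 12 weeks (9.6.1).
- Recruitment window: 1 March to 1 September 2020 (Synopsis), 184 days, 184/7 = 26.3 weeks.
- Halt length H: not stated. Values of 0, 4 and 8 weeks are assumed. Three 12-week halts would take 36 weeks and would not fit the window.
- Rate of falls during backwards walking: not given, so the results count further starts, not harm.

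**Maximum.** If the faller is in the batch being recruited and falls after start k of 5, then 5 − k = 4, 3, 2, 1 or 0 more can start. The maximum is 4/20 = 20%. If the faller is from a previous batch and still on programme when recruitment resumes, up to 5/20 = 25% can start. Someone who starts as a halt begins has 12 − H weeks left at resumption: 8 if H = 4, 4 if H = 8, and 0 if H = 12, when this case disappears.

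**Recruiting time per batch.** With three halts and equal batches, R = (26.3 − 3H)/4 = 6.6, 3.6 and 0.6 weeks for H = 0, 4 and 8. This is the longest wait for the next count. The gap between intervention starts is g = R/5 = 1.314, 0.714 and 0.114 weeks.

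**Mean, current batch up to the end of its halt** (even spacing, constant risk per programme-week). Between starts k and k + 1, k people are on programme and 5 − k starts remain.

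- Weighted starts: g(1×4 + 2×3 + 3×2 + 4×1) = 20g.
- Exposure: g(1 + 2 + 3 + 4) + 5H = 10g + 5H.
- Mean = 20g/(10g + 5H): 2.0 for H = 0; 14.3/27.1 = 0.5 for H = 4; 2.29/41.1 = 0.06 for H = 8.

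**Mean, all participants over their full 12 weeks.** Total exposure is 20 × 12 = 240 programme-weeks. For H = 4 and 8, the current batches contribute 4 × 20g = 80g. The five people from the preceding batch are on programme throughout the next recruiting period, and contribute 5 × (5 + 4 + 3 + 2 + 1)g = 75g in each of three batches, or 225g. The total is 305g.

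- H = 8: 305 × 0.1143 = 34.9; 34.9/240 = 0.15.
- H = 4: 305 × 0.7143 = 217.9. The last recruit of the batch before the preceding one also has 12 − (7.57 + 4) = 0.43 weeks left with 5 starts to come. This occurs twice and adds 2 × 5 × 0.43 = 4.3. Then 222.1/240 = 0.9.
- H = 0: each person's 12 weeks span 12/1.314 = 9.13 gaps. Summing the remaining starts over those gaps gives 270 + 3.9 for participants 1 to 10, 25 for the 11th, 90 for the 12th to 19th and 0 for the 20th, in all 388.9. Then 388.9 × 1.314 = 511.1, and 511.1/240 = 2.1.

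| Assumed halt | Mean, current batch | Mean, all participants |
|---|---|---|
| 0 weeks | 2.0 | 2.1 |
| 4 weeks | 0.5 | 0.9 |
| 8 weeks | 0.06 | 0.15 |

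**The case against.** The best defence is that the control is already tight for a single-site pilot of 40. Batches are small, recruitment resumes only if the team is satisfied, and a known fall would weigh in that decision. The Chief Investigator or treating clinician can act for the individual at once, and good clinical practice applies throughout. This stands, and it is why the point carries little weight. It does not remove the gap, because none of these provisions requires a study-level review when the event becomes known.

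Three stronger readings are tempting and are not supported:

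- *A reader might infer that the study cannot pause between counts.* Nothing in the plan prevents the Chief Investigator from pausing. The plan simply does not require it.
- *A reader might infer that about two more people would typically start after a fall.* That is the plain average of 4, 3, 2, 1 and 0, which treats each position in the batch as equally likely. If falls follow exposure, a mean near 2 arises only when halts take no time. With real halts, much of the exposure falls while recruitment is already stopped.
- *A reader might infer that home practice is unsupervised from the outset.* Section 9.6.1 sends the programme home only after the patient can complete it safely. It also starts at 5 minutes, sets an exertion target of 11 to 14 and lets the clinician regress it. Section 8.3 excludes people with weight-bearing restrictions, any neurological condition or registered visual impairment.

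One further objection shapes the remedy. Section 9.8 has the diaries collected at the 12-week visit, and review appointments number up to four. An event trigger alone would miss a fall that nobody mentions, so it needs a reporting instruction.

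**Conclusion.** The point holds as a modest gap in the safety rule. The one mandated study-level halt depends on recruitment count, later halts are worded around the newest five, and no event prompts a study-level review. The 4-of-20 maximum follows from the batch size alone. The 5-of-20 maximum also needs halts shorter than 12 weeks. The means rest on the planned window being kept, equal batches, even spacing, constant risk per programme-week and an assumed halt length. No probability of harm can be given, because the documents contain no rate of falls during backwards walking. The gap changes no sample size, outcome or analysis. It is a cheap improvement of low priority.

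**What to change.** Keep the count-based halts and add to sections 7 and 9.1:

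> Participants are told to report any injurious fall during backwards walking to their physiotherapist promptly, without waiting for diary collection, and physiotherapists ask about falls at each contact. Any such fall, or any SAE possibly related to the intervention, prompts the same study-team review at once, with new recruitment paused until it is done. Each review covers all participants still on the home programme, not only the latest five.

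The Chief Investigator decides. The unblinded team member already used for fidelity checks (section 9.8) prepares the review, so the outcome assessor stays blinded as section 9.5 requires. No committee is needed.

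The trigger should stay this narrow. Section 5 cites falls of up to 40% after knee and 36% after hip replacement, with no period stated. If those rates applied over the 12 weeks, 20 × 0.36 = 7.2 to 20 × 0.40 = 8.0 of the intervention arm would fall from any cause, and a trigger on any fall would stop the study too often.

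The cost is a short protocol amendment, an occasional extra review by existing staff and possibly a brief recruitment pause.

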8. PARTICIPANT IDENTIFICATION

8.1. Study Participants

Patients who have undergone either hip or knee arthroplasty will be eligible for inclusion if they meet the following criteria:

8.2. Inclusion Criteria

- Men and women aged 65 or older
- Participant is willing and able to give informed consent for participation in the study.
- Participants who have received a primary unilateral hip or knee arthroplasty due to osteoarthritis

8.3. Exclusion Criteria

- Post-operative weight bearing restrictions
- Post-operative complications such as infection, a deep vein thrombosis or pulmonary embolism, or failure of the wound to heal.
- Inability to undertake a backwards walking programme due to conditions such as severe cardiovascular or pulmonary disease (New York Heart Association III-IV).
- Severe dementia or communication difficulties that would prevent completion of study assessments.
- Any neurological condition.
- Further planned treatment on the same or contralateral hip or knee within next 6 months
- Registered as visually impaired

9. PROTOCOL PROCEDURES

9.1. Recruitment

Patients who have had a hip or knee replacement at the Nuffield Orthopaedic Centre in Oxford attend a 6 week post discharge clinic appointment. These patients will be screened for eligibility by their direct care team (Nuffield Orthopaedic Centre Physiotherapists). They will be introduced to the study by either a letter in the post from their direct care team (which will be sent alongside their clinic appointment letter) with information about the study and invitation letter and reply slip, or they will be introduced to the study and given the study information by their direct care team during their routine clinical appointment. Patients will be given ample time to consider taking part in the study. If they express an interest in the study the investigator will review the study details and answer any questions they may have. They will then be screened for eligibility and those who meet the criteria will take part in the study. If they agree to take part an appointment will be made to obtain consent and record baseline data and outcome measures with a trial research clinician at the Nuffield Orthopaedic Centre. Once patients have completed their baseline assessment they will be randomised according to the procedure set out below. Those who do not wish to take part will be asked if they can provide a reason for declining so that recruitment onto the trial can be analysed. The trial research clinician will also record the number of responders to the study information. As detailed in the study design section after the first 5 participants have been recruited to the intervention arm the study will stop whilst adverse event data is collected to ensure participants are not falling during the intervention. Providing this is not the case the study will resume and continue to stop and evaluate adverse event data for every 5 participants in the intervention arm.

9.2. Screening and Eligibility Assessment

The maximum time between screening and randomisation will be 2 months. During the screening process no exceptions will be made regarding eligibility and each participant must satisfy all the approved inclusion and exclusion criteria stated in section 8.

The healthcare professional that carried out the clinic appointment will screen the participant using the criteria provided. This will involve reviewing the patients' medical notes.

9.3. Informed Consent

Informed consent will be taken by an experienced physiotherapy researcher who has completed specific training in taking consent including Good Clinical Practice Training and has experience taking consent for participating in physiotherapy research.

The participant must personally sign and date the latest approved version of the Informed Consent form before any study specific procedures are performed.

Written and verbal versions of the Participant Information and Informed Consent will be presented to the participants detailing no less than: the exact nature of the study; what it will involve for the participant; the implications and constraints of the protocol; the known side effects and any risks involved in taking part. It will be clearly stated that the participant is free to withdraw from the study at any time for any reason without prejudice to future care, without affecting their legal rights, and with no obligation to give the reason for withdrawal.

The participant will be allowed as much time as wished to consider the information, and the opportunity to question the Investigator, their GP or other independent parties to decide whether they will participate in the study. Written Informed Consent will then be obtained by means of participant dated signature and dated signature of the person who presented and obtained the Informed Consent. A copy of the signed Informed Consent will be given to the participant. The original signed form will be retained at the study site.

